Carnitine Supplementation and Skeletal Muscle Function

22/06/2015

OBJECTIVE: To evaluate the effect of carnitine supplementation as the anti-inflammatory intervention for exploring the relationship between inflammation and associated with aging reduction of skeletal muscle mass;

DESIGN: Male and female volunteers over 60 years old are recruited to participate in the study (n=40). Subjects with diabetes, liver, or renal diseases and gastro-intestinal illnesses as well as all using vitamin supplements are excluded from the study group. The patients are randomly assigned to two experimental groups (n=20). All patients are subjected to consume gelatin capsules every day throughout the study. During the 24-weeks intervention period, Group A undergoes carnitine (1.5g) supplementation, whilst group B undergoes a placebo supplementation. Measurements are performed before, at the mid-point, and at the end of the intervention period (see primary and secondary output variables below).

METHODS:

- Plasma cytokines concentration Plasma cytokines (TNF-α, IL-1 and IL-6) as well as CRP is determined by enzyme immunoassay methods using high sensitivity commercial kits.
- *Biodex* The maximal isometric knee extensor peak torques is determined for all subjects by using a dynamometer to evaluate the relative changes in maximal force-generating capacity over the time course of supplementation. All subjects is familiarized with the testing protocol at least 2 weeks before testing baseline muscle strength measurements. To standardize the testing, subjects will have their shoulders strapped to the chair with adjustments for the back and hips and will perform each protocol in the sitting position. Each subject will perform three repetitions for the isometric contraction, with 90 s of rest between the repetitions (the subject's knee at an angle of 70°). The highest peak torque value is considered as the maximal value after recording for all repetitions.
- Octapolar bioimpedance analysis of body composition Each participant is weighted in accordance with the manufacturer's guidelines of the multifrequency analyzer. The contact with a total of 8 electrodes (2 for each foot and hand) gives the body composition analysis: dry lean mass, lean body mass, body fat mass, percent body fat and segmental lean analysis

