Carnitine Supplementation and Skeletal Muscle Function

NCT02692235

28/02/2017

Basic anthropometric characteristics of the subjects were evaluated as mean \pm SD. For educational and physical activity levels, a percentage of the total tested was used, while a frequency of meat consumption was presented as median and range. Changes in both groups across the supplementation time and ratios as well as changes in other measurements were analyzed with a Microsoft Excel (Microsoft Office) spreadsheet for the analysis of parallel-group controlled trials. For this, effects were interpreted using magnitude-based inferences. All data were log-transformed for analysis to reduce bias arising from non-uniformity of error; means of change scores in the placebo and l-carnitine groups, standard deviations of change scores, and effects (variations of change in both the means and their confidence limits (CL)) were back-transformed to percent units. Mean changes and effects were adjusted to the overall mean baseline value of the placebo and l-carnitine groups, by including the baseline value as a covariate in the analysis. Magnitudes of the effects were evaluated with the log-transformed data by standardizing the deviation of the baseline values of the placebo and l-carnitine groups. Threshold values for assessing magnitudes of standardized effects were 0.20, 0.60, 1.2 and 2.0 for small, moderate, large and very large respectively. Uncertainty in the effects was expressed as 90% CL and as probabilities that the true value of the effect was beneficial, trivial or harmful. These probabilities are not presented quantitatively but were used to make qualitative probabilistic clinical inferences about effects in preference to a statistical inference based on a null-hypothesis significance test. The effect was deemed unclear when the chance of benefit was sufficiently high to warrant the use of the treatment but the risk of harm was unacceptable. Such unclear effects were identified as those with an odds ratio of benefit to harm of <66 , a ratio that corresponds to an effect that is borderline possibly beneficial (25% chance of benefit) and borderline most unlikely harmful (0.5% risk of harm). All other effects were deemed clinically clear and the likelihood of the true effect as being trivial, beneficial or harmful was expressed with the following scale: 25–75%, possibly; 75–95%, likely; 95–99.5%, very likely; $>99.5\%$, most likely. To maintain an overall error rate of $<5\%$ to declare one or more changes as having opposite magnitudes (a substantial decrease instead of an increase, and vice versa), the effects were also evaluated as beneficial or harmful with a threshold of 1%, equivalent to the consideration of the overlap of substantial values with a 98% confidence interval (CI).

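### Does it matter that the SAP does not rank its odds-ratio rule and its 1% (98% interval) evaluation?

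*SAP*

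**What the plan says.** All the decision rules are in the single section of the SAP; the Protocol has none.

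- The odds-ratio rule comes first: "Such unclear effects were identified as those with an odds ratio of benefit to harm of <66". The SAP explains the cut-off as the point that is "borderline possibly beneficial (25% chance of benefit) and borderline most unlikely harmful (0.5% risk of harm").
- The remainder is assigned without qualification: "All other effects were deemed clinically clear", and these effects receive a likelihood word on a scale from *possibly* to *most likely*.
- The probabilities behind the words stay unpublished: "These probabilities are not presented quantitatively". The uncertainty that is shown is the 90% confidence limits.
- The last sentence adds that "the effects were also evaluated as beneficial or harmful with a threshold of 1" per cent, "equivalent to the consideration of the overlap of substantial values with a 98% confidence interval (CI"). Its purpose is an overall error rate below 5% "to declare one or more changes as having opposite magnitudes (a substantial decrease instead of an increase, and vice versa").

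The word *clear* is attached only to the odds-ratio rule. The 1% sentence speaks of evaluating effects as beneficial or harmful. The group size used below is in the Protocol, DESIGN: "The patients are randomly assigned to two experimental groups (n=20").

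**The concern.** Two criteria stand side by side with no order of precedence. The labels are used in place of a hypothesis test and the probabilities are not printed, so the label is the reported inference. If the criteria can disagree, a reader who sees *possibly beneficial* cannot tell whether the effect passed the 1% evaluation or only the odds ratio.

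The error statement adds to the worry. The rate below 5% is justified by the 1% evaluation. If a label rests on the odds ratio alone, that statement does not cover it, although a reader might assume that it does.

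**Working it through.** **Inputs.** From the SAP: cut-off 66; its basis of 25% benefit and 0.5% harm; 1% threshold; 98% interval; smallest substantial effect 0.20 SD; baseline as covariate. From the Protocol, DESIGN: 20 per arm. Residual degrees of freedom: 40 - 3 = 37 (two group means and one slope). Assumed, because the documents give no SD of change: the baseline-to-follow-up correlation r, varied from 0.3 to 0.9.

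**1. The SAP's own figures reproduce.** Odds ratio = (0.25/0.75)/(0.005/0.995) = 66.3, stated as 66. One tail of a 98% interval = (1 - 0.98)/2 = 1%, as stated.

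**2. The criteria are not equivalent.** On the odds-ratio boundary, odds(harm) = odds(benefit)/66:

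| Chance of benefit | Tolerated harm |
|---|---|
| 25% | 0.50% |
| 40% | 1.00% |
| 50% | 1.49% |
| 75% | 4.35% |

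They meet only at 40% benefit and 1% harm. This step needs no assumption from outside the SAP.

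**3. One example at the planned size.** With r = 0.3, SE = sqrt((2/20) x (1 - 0.3²)) = 0.302. For an observed +0.40 SD and a t distribution on 37 df:

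- Benefit = P(t > (0.20 - 0.40)/0.302) = 74.4%.
- Harm = P(t < (-0.20 - 0.40)/0.302) = 2.7%.
- Odds ratio = 104.6, so clear and *possibly beneficial*.
- 98% interval = 0.40 ± 2.431 x 0.302 = -0.33 to 1.13, which passes both -0.20 and +0.20.

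**4. What a reader can recover.** The 90% limits in this example are -0.109 to 0.909, a half-width of 0.509. The ratio of t quantiles is 2.431/1.687 = 1.44, and 0.509 x 1.44 = 0.733, which returns -0.33 to 1.13. With published limits in percent units, the step is done after taking logs. Placing ±0.20 SD on that scale also needs the baseline SD or the standardized effect.

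**5. How often the criteria part.** The simulation used 200,000 trials per setting, 20 per arm, baseline-adjusted. The 1% evaluation was failed when benefit and harm both exceeded 1%. The odds-ratio rule was taken jointly: unclear if benefit exceeds 25%, harm exceeds 0.5% and the ratio is below 66. At a true +0.2 SD:

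| r | Beneficial by odds ratio | of which fail at 1% (share of all trials) | as share of beneficial labels |
|---|---|---|---|
| 0.3 | 29.5% | 15.3% | 52% |
| 0.8 | 46.3% | 9.2% | 20% |
| 0.9 | 63.4% | 1.7% | 3% |

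At a true +0.6 SD the last column falls to 26%, 2.4% and about 0%.

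The opposite disagreement (unclear by odds ratio, passing at 1%) depends on how the first rule is read. At a true effect of 0 and r = 0.3, 0.8 and 0.9, it occurs in 0.00%, 0.09% and 1.02% of trials under the joint reading. If every ratio below 66 is called unclear whatever the chance of benefit, it occurs in 4.5%, 9.3% and 20.5%.

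**6. Wrong-direction labels.** At a true -0.2 SD, one effect is labelled beneficial by the odds ratio in 3.3% (r = 0.3) to 0.6% (r = 0.9) of trials. If both criteria are required, the range is 1.0% to 0.6%.

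**7. Reach of the 5% statement.** For k independent effects at 1% each, the overall rate is 1 - 0.99^k: 4.9% for k = 5 and 5.9% for k = 6. The SAP does not state k.

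**The case for a change.** The strongest case for a change is that the two natural readings give different labels from the same data. *Also evaluated* fits a check shown beside the label. The purpose of controlling an overall error rate fits a condition that the label must meet. At a low correlation the choice affects about half of the beneficial labels when the true effect is at the smallest substantial size. Rebuilding the 98% interval shows whether an effect would pass, but not which criterion produced the printed word. One sentence would settle it.

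The arithmetic of that case stands, and so does the absence of the sentence. Its force is limited in three ways:

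- The SAP does not define *clear* twice. Only the odds-ratio rule assigns labels, and it does so for all remaining effects; the 1% sentence comes afterwards, with its own purpose. An analyst would reasonably report the odds-ratio label and treat the 1% result as additional, in which case no label changes.
- The large frequencies belong to low correlations and to true effects at or below the smallest substantial size. They also depend on how the below-66 rule is read, and the documents settle neither r nor that reading.
- Requiring both criteria has a price. Counting every clear label, including trivial ones, the loss at a true effect of 0 is 52%, 58% and 57% of trials (r = 0.3, 0.8, 0.9) under the joint reading, against 7.4%, 3.9% and 0.7% under the literal one. Nor would it secure the 5% statement, which holds only up to about five independent effects.

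**Conclusion.** No change to the plan follows. The SAP leaves out one reporting detail: whether the printed label had to pass the 1% evaluation. The gap is genuine, because a *possibly beneficial* label can carry 0.5% to 4.3% harm at the odds-ratio boundary against 1%, and the example at +0.40 SD shows a real disagreement at 20 per arm. But the text gives a workable default, the odds-ratio label with the 1% result beside it. No data, estimate or interval depends on the choice, and a reader can rebuild the 98% interval. Imposing the 1% evaluation as a new condition would be a trade-off, not a correction.

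Two cautions help in reading the results. The error statement applies only to effects that passed the 1% evaluation, and only if about five or fewer independent effects are in view. How often the criteria differ rests on assumed correlations of 0.3 to 0.9 and on the reading of the below-66 rule; the 0.5% to 4.3% comparison rests on neither.

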- Plasma FFA and glycerol Plasma samples is taken in fasted state before starting and after finishing the training protocol. FFA and glycerol concentrations is determined by routine enzymatic spectrophotometric assays in the laboratory of prof. [name].
- Global Physical Activity Questionnaire Developed by WHO questionnaire for physical activity surveillance. It collects information on physical activity participation in three domains: activity at work, travel to and from places and recreational activities; as well as sedentary behaviour, comprising 16 questions.

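### The SAP's overall opposite-direction error rate below 5% is not assured: 1% per effect supports 5 independent effects (4 under any dependence), but 11 outcomes are listed and no smaller family is named

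*SAP*

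**What the plan says.** The last sentence of the SAP sets an overall error rate below 5% for a specific mistake, namely "to declare one or more changes as having opposite magnitudes (a substantial decrease instead of an increase, and vice versa"). The means is a 1% limit per effect: "effects were also evaluated as beneficial or harmful with a threshold of 1%, equivalent to the consideration of the overlap of substantial values", at the 98% level. Wording about one or more changes makes this a family-wise statement. The SAP does not say how many effects belong to the family.

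The scope of analysis is broad: "Changes in both groups across the supplementation time and ratios as well as changes in other measurements were analyzed" by the same method. Effects that are not unclear are then graded: "the likelihood of the true effect as being trivial, beneficial or harmful was expressed with the following scale", starting at 25% for possibly.

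The protocol's DESIGN section says "Measurements are performed before, at the mid-point, and at the end of the intervention period (see primary and secondary output variables below"), but no measure in the text that follows is labelled primary or secondary. METHODS lists TNF-alpha, "IL-1 and IL-6) as well as CRP is determined by enzyme immunoassay methods"; knee extensor peak torque; "dry lean mass, lean body mass, body fat mass, percent body fat and segmental lean analysis"; and FFA and glycerol.

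**The concern.** A limit on each effect becomes a limit on the family only once the family size is known. Holding 1% per effect below 5% overall requires four or five effects, and the documents list more than twice that number.

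This sentence is the plan's only multiplicity control, and it covers only wrong-direction declarations. The plan also replaces significance testing with qualitative likelihood terms and does not report the probabilities behind them. A reader therefore has little else to rely on, and is likely to take the 5% figure as applying to everything reported.

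**Working it through.** **Inputs.** From the SAP: overall rate below 5%, 1% per effect, 98% interval, smallest substantial effect 0.20 SD, possibly from 25%, unclear if the benefit-to-harm odds ratio is below 66. From the protocol: 20 per group, a mid-point and an end measurement, and the outcome list.

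**Per-effect figure.** (1 − 0.98)/2 = 0.01. The stated 1% reproduces. If a true effect lies at −0.20 or below, the lower 98% limit exceeds −0.20 with probability at most 1%, so a call in the positive direction has at most that probability. The mirror case is the same.

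**Overall figure for k effects.** Under any dependence the bound is k × 1%. If the effects are independent, the rate is 1 − 0.99^k.

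| k | Bound | Independent |
|---|---|---|
| 4 | 4% | 3.94% |
| 5 | 5% (not below 5%) | 4.90% |
| 6 | 6% | 5.85% |
| 11 | 11% | 10.47% |
| 20 | 20% | 18.21% |

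**Counting k.** Four inflammatory markers, one torque, four single-value body-composition measures and two lipid metabolites: 4 + 1 + 4 + 2 = 11. Segmental lean values and the SAP's ratios would add to this. The questionnaire is left out because the SAP summarises physical activity as percentages. If mid-point and end changes are declared separately, k is about 20: nine outcomes twice, plus FFA and glycerol once each, because METHODS says "Plasma samples is taken in fasted state before starting and after finishing the training protocol". That is 9 × 2 + 2 = 20.

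**What would lower the rate.** The ceiling needs every true effect to sit at the 0.20 boundary and every estimate to be imprecise enough to permit an opposite call. The correlations and standard errors below are assumptions; the documents give none.

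- *Trivial true effects* cannot be called in the opposite direction. The rate stays below 5% if at most 4 true effects are substantial (5 if independent).
- *Precision.* Take a true value of −0.20, baseline-to-follow-up correlation r, SE = √(2/20) × √(1 − r²), and 40 − 3 = 37 degrees of freedom. An opposite call needs an estimate above −0.20 + 2.431 SE and also above 0.20 − 0.681 SE (at least possibly). Both conditions meet at SE = 0.40/(2.431 + 0.681) ≈ 0.129; above that, the full 1% applies. Allowing for estimation of the SE:

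| r | SE | Per effect | × 11 |
|---|---|---|---|
| 0.80 | 0.19 | 1.00% | 11.0% |
| 0.90 | 0.14 | 0.73% | 8.1% |
| 0.92 | 0.12 | 0.44% | 4.8% |
| 0.95 | 0.10 | 0.04% | 0.4% |

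- *A stricter call*, requiring an estimate beyond 0.20, gives a bound for 11 effects of about 9.9% at r = 0.80 and 2.0% at r = 0.90.
- *Mixed precision.* If torque and the four body-composition outcomes have r = 0.95 and the other six stay at 1%, the bound is 6 × 1% + 5 × 0.04% = 6.2% at the end of treatment. With the mid-point added it is 10 × 1% + 10 × 0.04% = 10.4%.
- *Larger true effects*, with SE 0.20: about 0.51% per effect at a true 0.25 (5.6% for 11, 10.3% for 20) and 0.25% at 0.30 (about 2.7% and 5.0%).
- *Correlation between outcomes.* With a common correlation and all true effects at the boundary, the rate falls below 5% only above about 0.72 for 11 effects or 0.82 for 20.

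**The case against.** The strongest reply is that this is under-specification, not a wrong sum. The one conversion printed in the SAP is correct, and no printed figure contradicts the 5%. The count of 11 applies a 2015 methods list to a 2017 SAP that does not list its inferential outcomes, and a smaller family may be defined in a document not seen here. The count of 20 is weaker still: it infers separate mid-point declarations and relies on a sentence about a training protocol described nowhere else. The ceilings describe an unlikely configuration, since several body-composition measures overlap.

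The precision figures also omit the odds-ratio rule. With harm at 1%, a ratio of 66 requires benefit odds of 66 × 0.01/0.99 = 0.667, a 40% chance of benefit instead of 25%. For false beneficial calls this lowers the per-effect error to about 0.61% at r = 0.90 and 0.37% at r = 0.92, or about 6.7% and 4.1% for 11 effects.

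Much of this stands as qualification: the count of 20 is an inference, the ceilings are maxima, and the odds-ratio correction is right. It changes nothing material at r of 0.80 or below. None of it rescues the sentence. The SAP claims a family-wise rate, gives no family, and does not state the precision, effect sizes or correlation on which that rate would depend.

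**Conclusion.** The concern holds. The stated overall rate below 5% follows from the 1% threshold only for 4 effects under any dependence or 5 if independent. For the 11 outcomes listed, the documents support only an 11% ceiling (10.5% if independent). For about 20 effects the ceiling is 20% (18.2%).

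The actual rate may be above or below 5% and cannot be computed from the documents. The failure is in the assurance; it does not show that any declared effect is wrong. The limits of 4 and 5 need no assumption beyond the per-effect 1%. The conclusion for this trial needs only that more than five effects are evaluated, so it does not depend on the count of 20 or on any assumed correlation. The sentence should be corrected.

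**What to change.** Count every effect evaluated at the 1% threshold, including segmental lean values, ratios and each time point declared. State that number, k, in the SAP, and then do one of the following.

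- **(a) Restate the rate.** Replace the 5% figure with the bound k × 1%: 11% for 11 effects, 20% for 20. This changes wording only; the cost is a less favourable stated rate.
- **(b) Tighten the threshold** to just below 0.05/k. For 11 effects, 0.45% (99.1% interval) gives 11 × 0.45% = 4.95%. For 20, 0.24% (99.52% interval) gives 20 × 0.24% = 4.8%. With 37 degrees of freedom the multiplier rises from 2.431 to 2.757 or 3.001, so decision intervals widen by about 13% or 23%. The SAP is written in the past tense; if the analysis is done, the declarations must be re-run.
- **(c) Name the family.** Keep 1% for at most 4 named effects and label the rest exploratory. Fewer effects are then error-controlled. This is available only if the family was fixed before results were seen; otherwise use (a).
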